Pragmatic-Explanatory Continuum: The primary purpose of this trial is to inform clinical decision making. Therefore, according to the framework described by co-investigator [name] and other trial methodologists, this trial has been designed along the pragmatic end of the pragmatic-explanatory continuum.⁴⁹ Specifically, most study domains [eligibility criteria, follow-up intensity, primary outcome and primary analysis] will follow pragmatic approaches (“Does this intervention work under usual conditions?”); practitioner expertise and adherence and the flexibility of the interventions will follow approaches midway along the pragmatic-explanatory continuum (“Can this intervention work under ideal conditions?”). This protocol has been designed following the 2010 SPIRIT guidelines (Standard Protocol Items for Randomized Trials)⁵⁰ and results will be reported according to the 2008 CONSORT guidelines for pragmatic trials.⁵¹

METHODS

Study Setting: This study will occur at major tertiary care children’s hospitals. These sites were specifically chosen due to their size (they are among the largest children’s hospitals in Canada), relatively close proximity, and interest in collaborative work in improving outcomes in pleural empyema. These centres also preferentially use chest drain with fibrinolytics (as opposed to VATS) as their first line treatment of choice for pleural empyema in children. Furthermore, in all centres, most chest drain insertion is performed using an image guided percutaneous technique performed by interventional radiologists and have similar antibiotic prescribing patterns. Lastly, all centres are also implementing clinical pathways to standardize the management of this condition.

Eligibility - Inclusion Criteria:

1. age 6 months to 18 years
2. hospitalized with diagnosis of pleural empyema requiring chest tube drainage with fibrinolytics as judged by the attending physician with the following criteria:
 - (a) pneumonia with pleural effusion as documented on ultrasound of the chest; AND
 - (b) need for further intervention in addition to antibiotics based on clinical criteria [(persistent fever despite on antibiotics for at least 48 hours OR significant respiratory distress tachypnea, hypoxia) as a result of the pleural fluid collection]

Version June 29, 2017.

Eligibility - Exclusion Criteria:

1. empyema as a result of tuberculosis, fungus or non-infectious causes (e.g. malignancy)
2. known coagulation impairment

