- c) *Drain management* - Chest drain management will be at the discretion of treating physicians. Suggested management in the care pathway will include maintaining -20 cm H₂O of continuous suction and once daily flushes with 10 ml of normal saline (on days where no study drug is administered) to maintain patency.
- d) *Criteria for drainage removal* - Similarly, although recommendations for drainage removal will be made in the care map (< 1ml/kg/d), ultimately the decision to remove the chest drain will be made at the discretion of the responsible physician likely based on a gestalt of clinical parameters (amount of drainage, appearance of the child, fever, etc.). All patients will likely be initially on a similar regime of antibiotics and then tailored based on microbiologic results.
- e) *Diagnostic imaging* - There is no consensus on the type (ultrasound versus plain radiograph) or frequency of diagnostic imaging necessary after drain insertion in hospitalized children. Therefore, in contrast to the aforementioned adult RCT of DNase, follow-up radiographs will only be assessed as an exploratory outcome in the study protocol.

Outcomes - Primary outcome: *Time to hospital discharge:* This outcome is the most common outcome measure in trials of childhood empyema. This is defined as the time, measured in hours, and reported in days rounded to a single decimal point, from insertion of the chest drain to discharge from hospital. This will be assessed by a research assistant on a twice daily basis.

Outcomes - Secondary outcomes: Secondary outcomes include measures of effectiveness, harm and cost-effectiveness. Formal clinical follow-up and review of other parameters such as radiographic resolution and lung function testing will not be performed as preliminary work from this group of investigators and others suggests that long-term outcomes in childhood pleural empyema are almost universally positive. Our prospective cohort study has found that by six months, virtually all patients are asymptomatic and follow-up radiographs have normalized in 62/65 (95%) and pulmonary function tests normalize in 27/28 (96%).⁵²

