h. *Cost of the hospitalization*: An economic evaluation will compare the relative costs of DNase-tPA with tPA alone in previously well children who present with pleural empyema, using patient-level data from the trial. We will conduct the analysis from a hospital's perspective because hospital administrators will be making reimbursement decisions for this intervention. Since empyema is an acute condition and the long-term consequences are negligible, the time horizon of the analysis will be the length of hospital stay. Since the primary effectiveness outcome is length of hospital stay or time to hospital discharge, which can be expressed in monetary terms (i.e. hospitalization cost), we will only compare the costs of the two strategies to avoid double-counting the effectiveness. The cost of each patient includes the cost of intervention (DNase-tPA or tPA alone) and costs incurred during the hospital stay ("hospitalization cost"). We will obtain the hospitalization costs of each patient from case costing data from hospital financial departments. We will calculate mean cost per patient by intervention group, based on initial intervention assignment, and incremental cost using simple linear regression:

$$C_i = \alpha_i + \beta t_i + \varepsilon_i$$

Where C_i is the cost for each patient i , α is the intercept term, t is an intervention dummy term ($t=1$ if the patient received DNase-tPA and $t=0$ for tPA alone), and ε is the stochastic error term. The regression coefficient β estimates the incremental cost of DNase-tPA compared with tPA alone. The regression statistics will show mean cost per patient by intervention group and the uncertainty around the mean estimates. We will also conduct sensitivity analysis to assess the robustness of the results.

i. *Mortality*: this will include mortality from any cause during the hospitalization for empyema.

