Recruitment: All study patients will be initially identified by research assistants who will review both (a) all new admissions to the relevant inpatient units in each study centre twice daily; and, (b) all referrals for chest drainage insertion at each centre. It is anticipated that most drains at both sites will be inserted by interventional radiologists, although a minority may be inserted by general surgeons. Physicians and radiologists/surgeons will also be asked to notify the site research assistant and/or site investigator of children admitted with pleural empyema who may be eligible for the study. Patients will be approached, eligibility criteria confirmed, consent obtained, and enrolled after the decision to refer for chest drainage but before chest drain insertion occurs.

Randomization – Sequence generation, allocation concealment and implementation: After informed consent is obtained, patients will be randomized into treatment groups using a random allocation sequence facilitated by the Applied Health Research Centre (AHRC), which will be the coordination and management centre for the trial and administered by the hospital research pharmacies. Randomization will be stratified by centre. Blocking will be used to ensure that the two comparison groups are about the same size throughout the trial for each center and for the trial as a whole (about 49 per group). An allocation ratio of 1:1 with random block size will be used within each stratum (centre). This will help to ensure that clinicians, investigators, or outcome assessors will not decipher the block size. A computer-based pseudo-random number generator will be used to create treatment allocation tables for each study center. After patient eligibility has been confirmed and consent obtained and just as the patient leaves the inpatient unit to the radiology suite or operating room for chest drain insertion, the site investigator, or his/her delegate, will assign the patient a unique study identification (ID)

number in sequential order. The study ID will correspond with the randomization table held in the research pharmacy for dispensing blinded DNase or placebo. The biostatistician will maintain a secure master list of the randomization codes and the assigned treatments will be checked against the master list at the end of the study.

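### The cost outcome has no stated start point and on its plain reading includes pre-randomization inpatient costs, which the cost regression leaves unadjusted; the result is unbiased but less precise than it could be.

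*Combined protocol and SAP*

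**What the plan says.** All references are to the combined protocol and SAP.

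- **Outcomes – Primary outcome.** Time to hospital discharge runs "from insertion of the chest drain to discharge from hospital".
- **Outcomes – Secondary outcomes, item h (Cost of the hospitalization).** The horizon is set thus: "the time horizon of the analysis will be the length of hospital stay". Each child's cost is the intervention plus "costs incurred during the hospital stay". The source is hospital accounts: "We will obtain the hospitalization costs of each patient from case costing data from hospital financial departments". No start at drain insertion is given, and no rule removes earlier costs.
- **Same item, reason for comparing costs only.** The argument begins "Since the primary effectiveness outcome is length of hospital stay or time to hospital discharge", which presents the two periods as one measure.
- **Same item, model.** Cost is regressed on an intercept and a treatment indicator. An unspecified sensitivity analysis is also promised.
- **Eligibility – Inclusion Criteria.** Children must be "hospitalized with diagnosis of pleural empyema requiring chest tube drainage with fibrinolytics". One of two alternative clinical routes is "persistent fever despite on antibiotics for at least 48 hours"; the other is significant respiratory distress.
- **Randomization.** The study ID that fixes the allocation is assigned "just as the patient leaves the inpatient unit to the radiology suite or operating room for chest drain insertion".

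**The concern.** The primary outcome starts at drain insertion, while the cost outcome, read plainly, starts at admission. The gap between them falls before allocation, so treatment cannot change what is spent in it. Children will differ in the length of that gap, and a model with only a treatment term leaves the variation in the error. Three things follow:

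- the interval for incremental cost may be wider than it needs to be;
- with 49 children per arm, a chance difference in time to referral passes straight into the estimate;
- the arm mean costs describe a longer window than the primary outcome that the text says they express in money.

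The third point affects how hospital administrators, the audience named in the cost section, would read a percentage saving.

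**Working it through.** **1. The plan's own figure.** Inputs from Sample size: SD 2.9 days, difference 2 days, two-sided alpha 0.05, power 90%. The exact two-sample t-test gives power 0.899 at 45 per group and 0.905 at 46, so 46 is reproduced. With 5% added, 46 × 1.05 = 48.3, rounded up to 49. At 49 per group power is 92.2%. These figures concern the primary outcome and are not in dispute; the plan gives no sample size or SD for cost.

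**2. Does the earlier cost bias the comparison?** Let P be inpatient days before insertion and D days from insertion to discharge, so that whole stay is T = P + D. P is settled essentially by the time of allocation, so its expected value is equal in both arms. Hence E(T | DNase) − E(T | control) = E(D | DNase) − E(D | control). The expected treatment coefficient is the same for either window.

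**3. Effect on precision, P and D independent.** The documents give no SD for P; the values s = 1, 2 and 3 days are assumptions. Days stand in for cost at an equal daily rate. Var(T) = 2.9² + s², and removing P multiplies the interval width by 2.9 / √(2.9² + s²).

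| s (assumed) | Var(T) | Share due to P | Interval narrower by |
|---|---|---|---|
| 1 | 8.41 + 1 = 9.41 | 10.6% | 1 − 2.9/3.07 = 5.5% |
| 2 | 8.41 + 4 = 12.41 | 32.2% | 1 − 2.9/3.52 = 17.7% |
| 3 | 8.41 + 9 = 17.41 | 51.7% | 1 − 2.9/4.17 = 30.5% |

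**4. Effect if P and D are correlated.** With correlation r, Var(T) = 2.9² + s² + 2r(2.9)s. Cutting the window at insertion leaves variance 2.9² = 8.41. Keeping T and adjusting for P leaves 2.9²(1 − r²), which is 8.41 × 0.91 = 7.65 at r = ±0.3.

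| s | r | Var(T) | Cut at insertion: change in width | Adjust for P: change in width |
|---|---|---|---|---|
| 2 | −0.3 | 12.41 − 3.48 = 8.93 | √(8.41/8.93): −3% | √(7.65/8.93): −7% |
| 2 | +0.3 | 12.41 + 3.48 = 15.89 | √(8.41/15.89): −27% | √(7.65/15.89): −31% |
| 1 | −0.3 | 9.41 − 1.74 = 7.67 | √(8.41/7.67): +5% | √(7.65/7.67): about 0 |

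The last row shows why the covariate is the safer remedy. Cutting the window can lose precision when the correlation is negative. Adjustment does not, apart from one residual degree of freedom among 98 children.

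**5. Chance imbalance.** The SE of the between-arm difference in mean P is s√(2/49) = 0.202s.

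- Half a day or more, either direction: probability about 1%, 22% or 41% for s = 1, 2 or 3.
- One day or more: below 0.0001%, about 1.3%, or about 10%.

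**6. Mean costs.** Sample size quotes a mean post-insertion stay of 6.8 days. A 2-day saving is 2/6.8 = 29% of that. With an assumed 2 earlier inpatient days in the denominator it is 2/8.8 = 23%. The absolute saving is unchanged.

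**The case against.** The strongest reply is that randomization already protects the comparison. That stands. A reader might infer that the reported cost difference fails to correspond to the difference in stay. It does not fail: expected pre-insertion cost cancels (step 2), so the cost-only comparison survives the loose wording as far as the expected difference goes.

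Other replies also have weight:

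- **Hospital perspective.** Mean cost per admission is a legitimate quantity for administrators, so replacing it outright would be partly a matter of preference.
- **Possible intent.** The cost section uses the two terms interchangeably, so an insertion-to-discharge window may have been meant. The text would still need a start point, since a finance department asked for hospitalization cost may return the whole admission.
- **Assumed inputs.** The pre-insertion SD and its correlation with later stay are not in the documents. An equal daily rate may overstate the pre-insertion share, because drain placement under anesthesia, study drugs and further procedures fall at or after insertion.
- **Status.** Cost is secondary, the secondary analyses are described as hypothesis generating, and the trial is not sized on cost.
- **Partial cover.** Prior antibiotic and fever durations are collected at baseline, but neither is inpatient time and neither is in the cost model. The sensitivity analysis is not specified.

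Two further inferences are tempting and unsupported. A 1-day imbalance is not a likely scale: it has about a 1.3% chance at an assumed SD of 2 days. Nor do the documents mention intensive care before randomization, or say that the 48 hours of antibiotics are given in hospital. They show that children are inpatients when allocated, not for how long.

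**Conclusion.** The point holds as a low-severity improvement. The cost and primary-outcome windows differ on the plain reading, the text calls them one measure, and the cost model has no term for the part that precedes allocation. The incremental cost is unbiased. The harm is avoidable imprecision, exposure to chance imbalance, and arm mean costs on a different window from the primary outcome.

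The size cannot be fixed from the documents. Under independence, an assumed pre-insertion SD of 1 to 3 days puts the available narrowing of the interval at about 5% to 30%. At an assumed SD of 2 days, covariate adjustment would narrow it by about 7% if the correlation is −0.3 and about 31% if it is +0.3. All of these figures use days as a proxy for cost. If pre-insertion stay is short and uniform, the gain is negligible, and so is the harm.

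**What to change.** In Outcomes – Secondary outcomes, item h:

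1. State when the cost window starts. Keep whole-admission cost as the outcome if the hospital perspective calls for it.
2. Add inpatient days from admission to drain insertion, taken from the hospital record, as a covariate in the cost regression.
3. Where case-costing data are dated by service, also report cost from drain insertion to discharge. The documents do not say whether the sites can do this, so it should not be the only remedy.
4. Reword the sentence that equates length of stay with the primary outcome, so that the primary outcome is described as running from drain insertion.

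The cost is one extra data item per child, one extra model term and a few changed words. The sample size, the primary analysis and clinical care are untouched.

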Interventions: Patients will be randomized to receive either: (a) tPA [alteplase (Cathflo®), Roche] at a dose of 4 mg followed by a placebo (saline) administered intrapleural via chest drain once daily for 3 doses; or, (b) tPA at a dose of 4 mg followed by DNase [dornase alfa (Pulmozyme®), Roche] at a dose of 5 mg. Weight-based dosing will not be used for tPA or DNase, as pleural concentrations are unpredictable and variable. Pediatric studies of tPA^{29 31} and guidelines²¹ have utilized adult dosing. DNase will be constituted by the research pharmacies in clear liquids in a polyethylene syringe⁴². Since the stability of a tPA-DNase admixture is unknown, the drugs will be administered sequentially with a 1 hour indwelling time for each drug as described in the aforementioned adult trial. For tPA, the contents of the vial will be diluted to a total volume of 10 ml normal saline (tPA) for children less than or equal to 10 kg and 20 ml for children > 10 kg. A flush of 5 ml of normal saline will be instilled after drug administration. Following the instillation of tPA the drain will be clamped for one hour and then will be opened to drain under suction at a pressure of -20 cm H₂O for one hour. Then, either DNase or placebo will be instilled as a volume to 10 ml with normal saline for children less than or equal to 10 kg and 20 ml for children > 10 kg, followed by the same 5 ml normal saline flush, the same one hour period of clamping and the same one hour period of drainage at -20 cm H₂O. Thus in total, each cycle of tPA-study drug instillation and drainage will take 4 hours to complete. The pharmacies will prepare the two arms (DNase or placebo) in a manner such that both are identical (packaging, colour, volume, texture, and odour) to ensure blinding. The contents of the vials (tPA followed by DNase or placebo) will be instilled into the chest drain by clinicians caring for the child. The first dose of tPA will be given immediately (within 1 hour) after insertion of the chest drain by the interventional radiologist or surgeon in the procedure suite or by clinicians on the ward and DNase or placebo will be instilled on the ward. On the following day (day 1) and the subsequent day (day 2) a dose of tPA followed by the study drug will be administered in the morning, between 9 and 10 am, in a similar fashion. Thus, each patient will receive a total of three doses of either tPA or tPA-DNase over 48 hours.

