Clinical Samples at the Hospital for Sick Children: At the SickKids site only, consent will be obtained to store samples of chest tube drainage from subjects. These samples will be used for future testing to determine the microbiological cause of empyema.

Concomitant Medication: Patients in either arm will not receive any intrapleural drug other than directed from this study.

Criteria for discontinuing study interventions: Patients who develop anaphylaxis or serious bleeding (requiring a blood transfusion or resulting in a hemoglobin drop of ≥ 20 g/L) while receiving study interventions will not receive further study drugs. Patients whose chest drains is displaced will only be replaced if clinically indicated for pleural fluid drainage and not for study drug administration alone. Outcomes for all patients who do not received the full study interventions will be analyzed in the group they were assigned to.

Standard care: In keeping with a pragmatic-type trial design, all children will receive standard care for this condition including supportive care, laboratory investigations, imaging, antibiotics, chest drain care and removal and discharge as outlined in the standard care guidelines. Although some variability is expected in care among treating physicians, rigorous randomization and blinding should ensure that confounders are equally distributed between groups. A detailed care map will be adapted from the existing clinical practice guideline co-authored by team investigators (EC and SM) together with the Canadian Pediatric Society. Specific elements in the care plan include:

- a) *Antimicrobial management* - Patients in both treatment arms will receive standard therapy for pleural empyema in children as directed by the responsible physician and standardized guidelines. All participating hospitals currently recommend a 2nd or 3rd generation cephalosporin (cefuroxime or ceftriaxone or cefotaxime) as the empiric antimicrobial therapy with possible addition of clindamycin or vancomycin if *S. Aureus* is a suspected etiology. It is expected that antibiotic regimens will be tailored in line with local microbiology advice.
- b) *Drain insertion* - Chest drains will be placed using an image guided percutaneous technique by interventional radiologists or by a surgeon using a standardized technique under anesthesia agreed upon by all sites. The recommended size of catheter drain used will be an 8 or 10 French pigtail catheter.

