Primary outcome: Data will be analyzed according to intention to treat principles for the primary outcome (e.g. patients who do not receive all three doses of study drug will be analyzed in the group they were assigned to). Exceptions to this principle will only include any patient who dies in hospital and will be excluded from the analysis of time to hospital discharge. Given that the primary outcome and other acute secondary outcomes are obtained during hospitalization, it is anticipated that there will be no missing data for these outcomes with the possible, but unlikely exception of in-hospital death, which is rare in childhood empyema. For the follow up outcomes at 3 months, the proportion of patients who follow up will be presented for each treatment arm, and patients who are lost to follow up will be stated but omitted from the analysis. The primary outcome, time (in days) to hospital discharge, will be described as the difference between the two means with the 95% confidence intervals. The student's t-test (independent two sample test assuming equal group size and variance), will be used to detect a difference between the two treatment groups. If the resulting data is inappropriate for a t-test (increasing variance with the mean is the biggest concern since the test is quite robust to non-normality in the population), a suitable transformation or non-parametric test may be used. If feasible, a secondary analysis of the primary outcome will analyze time to discharge, treating death as a competing risk, using methods for survival data. Since randomization is stratified between five centres, the analysis will adjust for this stratification by including centre as a covariate in a multiple linear regression model, to obtain adjusted treatment effects. Additionally, a treatment by centre interaction will be tested to see if the treatment effect differs between centres. Subgroup analyses will also be conducted to explore any potential differences in outcomes by age or sex.

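### Minor: the cost regression omits centre, the stratification factor. This does not bias the incremental cost but can make its interval too wide; the treatment indicator should also be worded by assignment.

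*Combined protocol and SAP*

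**What the plan says.** All references are to the combined protocol and SAP.

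- **Cost model** (Outcomes - Secondary outcomes, item h). Mean cost per arm is calculated "based on initial intervention assignment, and incremental cost using simple linear regression". The printed equation has an intercept, one treatment dummy t and an error term. The coefficient of t is the incremental cost. The intercept is printed with a patient subscript, but the text calls it the intercept term, so it is not a centre effect.
- **Cost data** (same item). Each patient's hospitalization cost is taken from "case costing data from hospital financial departments". A sensitivity analysis is promised, but its content is not given.
- **Randomization**. "Randomization will be stratified by centre", at 1:1 with random block sizes within each centre.
- **Centre adjustment** (Statistical Analysis, Primary outcome). Because of the stratification, "the analysis will adjust for this stratification by including centre as a covariate in a multiple linear regression model". Nothing extends this to cost.
- **Definition of t** (item h). t equals 1 "if the patient received DNase-tPA", although the same item groups patients by initial assignment. Under Criteria for discontinuing study interventions, patients who do not get the full interventions "will be analyzed in the group they were assigned to".

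**The concern.** The plan accepts, for its primary outcome, that a factor used to stratify randomization should be in the model. The cost model leaves that factor out. Cost is also the outcome for which a hospital effect can most easily be imagined, because the figures come from hospital accounting. The Study Setting section describes similar clinical practice and shared pathways across sites, which may limit differences in care, but it does not address how a stay is costed.

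What is at stake is precision. Lower cost with DNase-tPA is a stated secondary hypothesis, and item h names hospital administrators as the users of the result and promises the uncertainty around the means. If hospitals differ in cost, the planned model overstates that uncertainty.

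The definition of t is a smaller matter of wording. Assignment and receipt differ only for a child who got no DNase despite being assigned to it, or who got the wrong drug. The documents leave room for the first case: "the drugs will be administered sequentially with a 1 hour indwelling time for each drug", with tPA first, and a displaced drain "will only be replaced if clinically indicated for pleural fluid drainage and not for study drug administration alone".

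**Working it through.** **Inputs from the documents.** Five centres; 1:1 random blocks within centre; 49 per group, so N = 2 × 49 = 98 (Sample size). The documents give no cost SD, no between-hospital cost variance and no power for cost, so there is no planned cost figure to reproduce. As background, the sample size does reproduce: SD 2.9 days, difference 2 days, two-sided 0.05 and 90% power give 45.17 per group by the exact t calculation, hence 46. Then 46 × 1.05 = 48.3, hence 49.

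**Input assumed.** Let p be the share of cost variance, apart from treatment, that lies between centres: p = B / (B + W), where B is the between-centre and W the within-centre variance. The values tried are 0, 5, 10, 20 and 30%.

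**Step 1: bias.** With allocation balanced within centre, each centre contributes about equally to both arms, so centre effects cancel from the difference in means. The unadjusted difference is unbiased.

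**Step 2: width.** The true variance of that difference is then about 4W/N. The one-term regression leaves B in its residual and so estimates 4(B + W)/N. The ratio of interval widths, without centre to with centre, is

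√[(B + W)/W] = 1/√(1 − p).

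| p | 1/√(1 − p) | Interval too wide by about |
|---|---|---|
| 0 | 1.000 | 0% |
| 0.05 | 1.026 | 3% |
| 0.10 | 1.054 | 5% |
| 0.20 | 1.118 | 12% |
| 0.30 | 1.195 | 20% |

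**Step 3: simulation.** 98 children, five centres, random blocks of 2, 4 and 6 within centre, 3,000 runs per setting. Normal and skewed costs were used with nearly equal centres, and normal costs with unequal centres (34/24/20/12/8). The width ratios were 0.999, 1.025–1.026, 1.054–1.055, 1.119–1.121 and 1.197–1.200, in line with the formula. Coverage of the nominal 95% interval without centre rose from 0.941–0.955 at p = 0 to 0.979–0.982 at p = 0.30. With centre it stayed at 0.941–0.956. The mean estimate was −0.49 to −0.51 with or without centre, against a true value of −0.5.

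A separate run under no treatment effect (4,000 runs, blocks of 2 and 4) gave a type I error for the nominal 5% test of 4.5, 3.8, 4.0, 2.9 and 2.0% without centre, and 4.5, 4.4, 5.3, 5.1 and 4.7% with it.

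**Step 4: other ways to express hospital differences.** If the share is read as an intraclass correlation, with centre effects drawn at random, the excess width is about 0, 2, 4, 9 and 15%. If each hospital multiplies cost by a factor with a coefficient of variation of 0, 10, 20 or 30%, it is about 0, 2, 8 and 16%. That last case takes stays of 6.8 versus 4.8 days with SD 2.9.

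**Step 5: one trial rather than the average.** Incomplete last blocks leave small imbalances within centre, so the two estimates agree on average but not exactly in a given trial. The typical difference (SD) was 4–5% of a standard error with no centre effect and 13–14% at p = 0.30.

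**Step 6: price of adjustment.** Residual degrees of freedom fall from 98 − 2 = 96 to 98 − 6 = 92. With no centre effect the adjusted interval was 0.1 to 0.2% wider.

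**The case against.** The plan is valid as written. An unbiased estimate with a conservative interval does not inflate the risk of a false claim of a cost difference, and the plan treats its secondary analyses as hypothesis generating. Regression on one dummy is numerically the equal-variance t-test that the plan uses for its other continuous secondary outcomes, and those omit centre too. That hospital finance departments cost differently is an inference, and nothing in the documents favours a share of 20–30% over 0–5%. The planned sensitivity analysis could include centre. A plain difference in mean cost is a defensible choice for a hospital-perspective analysis, and with centre terms the regression no longer yields the arm means that item h promises. All of this stands and keeps the point at the lowest grade. It does not remove an almost free gain in precision, and a sensitivity analysis that does not name centre cannot be counted as including it.

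A reader might infer more in three ways, and the documents support none of them:

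- **That omitting centre biases the incremental cost.** Blocked 1:1 allocation within centre rules this out.
- **That cost will be analysed as treated.** Item h groups patients by initial assignment and says the regression will show the means of those groups, which is so only if t codes assignment. The rule for patients not fully treated points the same way, so the word *received* is loose drafting.
- **That hospitals are known to differ in cost.** The documents give no such figure.

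**Conclusion.** The point holds as a minor improvement in precision. The interval for incremental cost is too wide by about 0 to 20% over assumed centre shares of 0 to 30%, and the size of the gain rests wholly on that assumption. If hospitals do not differ in cost, nothing is lost under the present model. The result also rests on allocation staying close to 1:1 within centre, as planned. No numerical effect is claimed for the definition of t, because the documents give no frequency for children who do not receive the assigned drug. The primary analysis and the sample size are untouched.

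**What to change.** In item h, change *simple linear regression* to *linear regression*, and replace the model and the definition of t with:

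> C_i = α + β·t_i + centre indicators + ε_i, where t = 1 if the patient was assigned to DNase-tPA and t = 0 if assigned to tPA alone. Centre is included because it is the stratification factor for randomization.

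With centre terms, α is no longer the tPA-alone mean. Report the raw mean cost per arm beside the centre-adjusted β, and note that the raw difference need not equal β exactly.

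The change uses four degrees of freedom and needs no new data. The rewording of t costs nothing.
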